2.3 Sample Size

The trial is powered for the comparison between the COV.EXPECT group and the TAU group. The type one error (alpha) is not adjusted for multiplicity due to the closed testing principle. A between-group effect size of d=0.5 is expected between COV.EXPECT and TAU for the change from baseline in the PHQ-15 score at 3 months. To detect this effect with a power of 80% and using a two-sided alpha of 5%, 64 patients in each group will be required, resulting in a total sample size of N=192. Assuming a loss to follow-up between baseline and 3 months (time point for primary outcome) of 25%, this results in N=258 randomised patients. Assuming that 50% of the screened patients meet the inclusion criteria, a total of N=516 patients will be assessed for eligibility.

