3.1 Confidence Intervals and P Values

For the primary analysis, the significance level is α =0.05 (two-sided). All further analyses are exploratory and will not be adjusted for multiplicity. All applicable statistical tests will be two-sided. All reported confidence intervals (CI) are at 95% level and two-sided.

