5.3 Efficacy Evaluation

5.3.1 Analysis of Primary Endpoint(s)

The analysis of the primary endpoint is based on the FAS and thus is as close as possible to the ITT principle.

The primary outcome is analysed with a linear mixed effects model with the change from baseline of the PHQ-15 score at 6 weeks and 3 months as dependent variable, treatment group (COV.EXPECT, COV.SUPPORT, and TAU), time (categorical: 6 weeks and 3 months), the stratification variable gender as well as baseline PHQ-15 as fixed effects and patient as random effect. Further, the interaction between time and random group is included and will be excluded from the model if the test result of the interaction is p≥0.05. If the interaction remains in the model, the respective contrast at 3 months will be explored further. If it is removed from the model, the overall treatment effect remains stable over time and can also be interpreted as the effect at the interesting time point 3 months.

The estimation will be performed using Maximum-Likelihood estimation with an AR(1)-structure for residual errors.

For the primary hypothesis, the global treatment effect will be tested first using the F-Test (two-sided). If the p-value is < 0.05, the contrasts in change for COV.EXPECT vs. TAU and COV.SUPPORT vs. TAU at a 5% level (two-sided) will be tested using the Wald test. Because of the closed testing principle an adjustment of the contrast p-values for multiplicity is not necessary. Mean difference estimates together with 95% confidence intervals will be reported.

After final database closure this analysis is repeated with an analogous model that further includes the measurement of the 6 months follow-up. The 3-months estimates from this model will only be interpreted as sensitivity analyses of the primary endpoint analysis.

The assumptions regarding normality of residuals are examined graphically. Histograms and quantile-quantile plots are used to evaluate normality of residuals. In case of unmet assumptions data can be transformed accordingly.

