5.3.2 Analysis of Secondary Endpoint(s)

The analysis of the secondary endpoints is based on the FAS and thus is as close as possible to the ITT principle. Missing values are not imputed, but the implicit MAR assumption of the analysis model will be used.

Continuous endpoints (PHQ-15, CFS, PDI, PHQ-15 PAIS) are analysed analogously to the primary endpoint. Mean changes for the respective time points together with 95% confidence intervals will be presented.

Dichotomous endpoints (Improvement of Long COVID symptoms, DSQ-PEM, DSM-5, B-IPQ) will be analysed with a mixed logistic model analogously to the linear mixed model used for primary analysis, except that the dependent variable is not the change from baseline, but the endpoint measurement at the respective time point. The improvement of Long COVID symptoms will further be displayed descriptively in the categories improvement, no change, and worsening over time by group.

Version 1.0 Page 14 of 18

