5.3.3 Risk factor regression analyses

To identify risk factors for the persistence of somatic symptoms in Long COVID we will use longitudinal data from the control group (TAU) within the FAS. Patients from the intervention group (COV.EXPECT, COV.SUPPORT) are excluded because the treatment could bias the results. The risk factors are analysed with a multivariable mixed linear regression with symptom persistence (PHQ-15) as outcome and different risk factors as independent variables, while taking the number of predictors with respect to the sample size into account. The list of possible risk factors includes:

- Age
- Gender
- Chronic physical diseases (SCQ-D)
- BMI
- Smoking
- Education
- Migration background
- PHQ-15 Baseline score
- Depression severity (PHQ-9)
- Illness-related worries (Whiteley-Index-7 [WI-7])
- Expected symptom severity in 6 months (NRS)
- Expected coping with symptoms in 6 months (NRS)
- Catastrophizing (Coping Strategies Questionnaire-Catastrophizing Subscale [CSQ-CAT])
- Illness perception (B-IPQ)
- Life stressors (Perceived Stress Scale-10 [PSS-10])
- Somatosensory Amplification (Somatosensory Amplification Scale [SSAS])
- Alexithymia (Toronto Alexithymia Scale-20 [TAS-20])
- Emotion regulation (Emotion Regulation Questionnaire [ERQ] suppression scale)
- Adverse childhood experiences (Adverse Childhood Experience Questionnaire German version [ACE-D])
- Stigmatization (Stigma)

In case of no significant effects of the interventions on the outcome PHQ-15 in the primary analysis (within the testing of the global effect) an additional analysis will be conducted within observations from all three groups. In the specified risk factor regression model the intervention group (TAU, COV.EXPECT, COV.SUPPORT) will be included as an adjusting variable.

Common risk factors for somatic symptom persistence:

The disease-specific regression analysis from the model to identify risk factors for Long COVID symptoms will be compared to models from the research Unit SOMACROSS to identify shared risk factors across conditions. Also further exploratory analysis should be conducted.

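### ML estimation with Wald contrasts and no degrees-of-freedom method makes standard errors in the primary mixed model about 1% too small; the risk-factor model has no stated method

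*SAP*

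**What the plan says.** SAP section 5.3.1 fixes the estimation method for the primary model: "The estimation will be performed using Maximum-Likelihood estimation", with AR(1) residuals. For inference, "the global treatment effect will be tested first using the F-Test (two-sided"), and if it is significant the COV.EXPECT and COV.SUPPORT contrasts against TAU "at a 5% level (two-sided) will be tested using the Wald test". Neither test is given a denominator degrees-of-freedom method, and the Wald test is given no reference distribution. Section 5.8 allows three software packages, so their defaults do not settle the matter.

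The specification reaches further by the SAP's own wording. Section 5.3.2 says "Continuous endpoints (PHQ-15, CFS, PDI, PHQ-15 PAIS) are analysed analogously to the primary endpoint". Section 5.3.5 repeats the primary analysis in the per-protocol set, and section 5.3.6 runs interaction tests for 16 subgroup variables inside the primary model. Section 3.1 adds: "All reported confidence intervals (CI) are at 95% level and two-sided".

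Section 5.3.3 is different. It says "The risk factors are analysed with a multivariable mixed linear regression with symptom persistence (PHQ-15) as outcome", restricted to TAU patients, but names neither ML nor Wald. It lists 20 possible risk factors and says that the number of predictors will be weighed against the sample size, without giving a limit or a selection rule.

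**The concern.** ML estimates the variance components as though the fixed effects were known. For an effect that varies between patients, this amounts to dividing the between-patient sum of squares by n instead of n minus the number of between-patient coefficients p. Standard errors come out too small. A Wald test read against the normal distribution adds a second, smaller error in the same direction, because it treats the variance as known.

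The confirmatory contrast tests are stated at 5% and the intervals at 95%, and both miss on the liberal side. The shortfall grows with p/n. It is therefore slight in the primary model, but could be material in a model with many predictors fitted to one arm, which is the setting of section 5.3.3.

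**Working it through.** **Inputs from the SAP.** Section 2.3: d = 0.5, two-sided alpha 5%, power 80%, 64 patients per group (192 in total), 25% loss to follow-up, 258 randomised, so 86 per arm. Section 5.3.1: between-patient coefficients are the intercept, two for group, gender and baseline PHQ-15, so p = 5. Section 5.3.3: TAU arm only (64 evaluable to 86 randomised), 20 candidate factors.

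**The plan's own figure.** The noncentral t calculation for d = 0.5 gives power 0.7952 with 63 and 0.8015 with 64 per group, hence 64. Then 64/0.75 = 85.3, rounded up to 86, and 3 × 86 = 258. The sample size is reproduced. The SAP gives no figure for coverage.

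**Formulas** (balanced, between-patient effects):
- SE ratio, ML to REML: r = √((n − p)/n).
- Actual error of an ML Wald test with normal reference: P(|t with n − p df| > 1.96 r).

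**Primary model, p = 5**

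| n | r | SE too small by | Critical value 1.96 r | Actual error |
|---|---|---|---|---|
| 192 | √(187/192) = 0.9869 | 1.3% | 1.934 | 5.46% |
| 258 | √(253/258) = 0.9903 | 1.0% | 1.941 | 5.34% |

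These are errors for one contrast without the preceding F-test. With a t reference on n − p df in place of the normal, they are 5.3% and 5.2%. REML with a normal reference gives 5.15% and 5.11%; REML with a t reference is exact in this balanced case.

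Simulation (6000 data sets per setting; random intercept, intraclass correlation 0.6, independent residuals in place of AR(1)) gave ML coverage of 94.4 to 94.7%, in line with the formula.

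**Effect of the F-test gate.** I simulated 192 patients with ML variance, an F reference on 2 and 187 df, and normal-reference contrasts. Under the global null, the F-test rejects in 5.4%, any false contrast passes in 4.5%, and COV.EXPECT against TAU passes in 2.7%. If COV.SUPPORT truly works (d = 0.5) and COV.EXPECT does not, the gated COV.EXPECT error is 5.4%.

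**Risk-factor model, if ML with normal Wald tests were used in TAU alone** (p = intercept plus predictors)

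| n | Predictors | r | SE too small by | Error per predictor |
|---|---|---|---|---|
| 64 | 6 | 0.9437 | 5.6% | 7.0% |
| 86 | 8 | 0.9462 | 5.4% | 6.7% |
| 64 | 10 | 0.9100 | 9.0% | 8.0% |
| 86 | 20 | 0.8694 | 13.1% | 9.3% |
| 64 | 20 | 0.8197 | 18.0% | 11.6% |

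Simulation (3000 data sets per setting, three visits, predictor correlation 0.3) gave ML coverage of 92.9% (n = 64, 6 predictors), 93.5% (n = 86 with 25% dropout, 8 predictors), 90.6% (n = 86, 20 predictors; 90.2% with 25% dropout) and 88.5% (n = 64, 20 predictors). The additional three-arm model with all 20 factors plus group (p = 23) would run at 6.8% (n = 192) to 6.3% (n = 258).

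**The case against.** Four points can be made for the plan.

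1. **The primary effect is negligible.** This largely stands. The inflation is at most about half a percentage point, and under the global null the F-test gate holds the COV.EXPECT error below 5%. The gate gives no such protection when the other intervention works.

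2. **The normal reference is assumed.** This also stands: the SAP names none. With a t reference the ungated error falls to 5.2 to 5.3%. The standard-error bias remains, and leaving the reference to the software is itself part of the defect.

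3. **ML may have a purpose.** Section 5.3.1 drops the time-by-group interaction at p ≥ 0.05 without naming the test. A likelihood-ratio test of a fixed effect needs ML fits, so one cannot say that nothing in the plan needs ML. That would justify ML for this one comparison, not for the reported estimates.

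4. **The SAP contains no 20-predictor ML model.** This stands. A reader might infer that 5.3.3 commits to fitting all 20 factors by ML, and so to a test of roughly 10%. The text does not support that: it names no method, calls the factors possible ones and promises to limit their number. Hypotheses 2 and 3 are exploratory under section 1.2, and section 3.1 treats everything beyond the primary analysis as exploratory, so no confirmatory claim depends on these p-values.

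A reader might also infer that every interval in the report is too narrow. That goes too far: the mixed logistic models of 5.3.2 have no estimated residual variance, and the mediation analyses of 5.3.4 are not governed by the sentence in 5.3.1.

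**Conclusion.** The point holds as a minor one. In the primary model, and in the linear mixed models that the SAP derives from it, the stated method gives error bars that are slightly too narrow. For the primary model the standard errors are 1.0 to 1.3% too small, with an ungated contrast error of 5.3 to 5.5% under a normal reference. This is unlikely to alter the primary conclusion.

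For section 5.3.3 the finding is conditional: the estimation method and the predictor limit are open. If the 5.3.1 approach were carried over, error per predictor would be about 7 to 8% with 6 to 10 predictors, and 9 to 12% as the worst case with all 20. Data-driven selection would add undercoverage that these figures leave out.

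The figures rest on the balanced between-patient formula. The simulations that support it used the assumed correlations given above and independent residuals, not AR(1).

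**What to change.** State once, for all linear mixed models (5.3.1, 5.3.2, 5.3.3, 5.3.5 and 5.3.6), that estimation is by REML with Kenward-Roger (or Satterthwaite) degrees of freedom, that the global test uses the F distribution, and that contrasts and intervals use the t distribution. Name the test for the time-by-group interaction; if it is a likelihood-ratio test, use ML for that comparison only and refit by REML for reporting. In 5.3.3, also fix the maximum number of predictors and how they are chosen, because REML does not close that gap.

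The cost is a sentence or two in the SAP. Primary-model intervals become wider by 1.9727/(1.96 × 0.9869) = 1.020 at n = 192, about 2%, and by about 1.5% at n = 258. The sample size needs no change, since the 64 per group already comes from a t-based calculation.

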5.3.2 Analysis of Secondary Endpoint(s)

The analysis of the secondary endpoints is based on the FAS and thus is as close as possible to the ITT principle. Missing values are not imputed, but the implicit MAR assumption of the analysis model will be used.

Continuous endpoints (PHQ-15, CFS, PDI, PHQ-15 PAIS) are analysed analogously to the primary endpoint. Mean changes for the respective time points together with 95% confidence intervals will be presented.

Dichotomous endpoints (Improvement of Long COVID symptoms, DSQ-PEM, DSM-5, B-IPQ) will be analysed with a mixed logistic model analogously to the linear mixed model used for primary analysis, except that the dependent variable is not the change from baseline, but the endpoint measurement at the respective time point. The improvement of Long COVID symptoms will further be displayed descriptively in the categories improvement, no change, and worsening over time by group.

Version 1.0 Page 14 of 18

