1.3 Study Endpoint(s)

Primary endpoint:

 Change from baseline in overall somatic symptom severity at 3 months measured with the sum score of the Patient Health Questionnaire 15 (PHQ-15)

Secondary endpoints:

- Change from baseline in overall somatic symptom severity at 6 weeks and 6 months measured with the PHQ-15
- Subjective improvement of Long COVID symptoms (improved vs. stable / worsened) at 6 weeks, 3 months, and 6 months
- Change from baseline in fatigue measured with the Chalder Fatigue Scale (CFS) at 6 weeks, 3 months, and 6 months
- Change from baseline in pain measured with an adapted version of the Pain Disability Index (PDI) at 6 weeks, 3 months, and 6 months

Version 1.0 Page 7 of 18

- Post-exertional malaise measured with the DePaul Symptom Questionnaire Post-Exertional Malaise (DSQ-PEM) at 6 weeks, 3 months, and 6 months
- Change from baseline in long COVID symptoms measured with the Patient Health Questionnaire-15 Post-Acute Infection Syndromes (PHQ-15 PAIS) at 6 weeks, 3 months, and 6 months
- Somatic symptom disorder evaluated with the Structured Clinical Interview for the Diagnostic and Statistical Manual of Mental Disorders, Fifth Edition (DSM-5) (SCID-5) at 3 months
- Change from baseline in symptom perception measured with the Brief Illness Perception Questionnaire (B-IPQ) at 3 months and 6 months

Mediator variables (all variables are measured at BL, 6 weeks, 3 and 6 months):

- Illness-related anxiety measured with the Somatic Symptom Disorder B Criteria Scale (SSD-12)
- Treatment expectations measured with the Treatment Expectation Questionnaire (TEX-Q)
- Expectation of symptom severity, of symptom burden, and of coping with symptoms measured with the European Network to improve diagnostic, treatment and health care for patients with persistent somatic symptoms (EURONET SOMA) Numeric Rating Scales (NRS)

Version 1.0 Page 8 of 18

2 Study Methods

In this chapter, a summary of the basic study methods is provided.

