2.2 Randomisation

Patients are randomised to COV.EXPECT, COV.SUPPORT or TAU with an allocation ratio of 1:1:1. The randomisation is stratified by sex with a block randomisation procedure with varying block length. The randomisation list was generated using R software (R Project for Statistical Computing) by an independent member of the biostatistics unit and uploaded in REDCap (Research Electronic Data Capture), a software for building and managing online surveys and databases.

The randomisation is performed directly after verification that no inclusion criteria are violated and no exclusion criteria are met. Baseline data are collected afterwards.

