5.1.1 Demographics and Baseline Characteristics

The following demographic and other baseline characteristics will be summarised in total and by randomised treatment as described in 5.1 in the FAS and PP set:

- Age in years
- Gender (male/female/divers)
- Duration of Long COVID
- Number of SARS-COV-2 infections
- Treatment setting of SARS-CoV-2 infections (At home, outpatient/At least one time in hospital on a normal ward)
- Number of SARS-COV-2 vaccinations
- Number of pre-existing physical conditions (Self-Administered Comorbidity Questionnaire [SCQ-D])
- Body mass index in kg/m²
- Migration background (yes/no)
- Permanent partner (yes/no)
- Number of people living in household
- Years of formal education (Lower education/Higher education)
- Occupational status (Full-time employed/Part-time employed/Stay-at-home/Unemployed or job seeking/Retired (pension)/Retired (disability)/School, training, studying/Parental leave/Other)
- Current sick leave (No/Yes, shorter than 6 weeks/Yes, longer than 6 weeks)
- Number of appointments with the doctor in the last 6 months
- Current intake of medication (yes/no)
- Smoking (yes/no)
- Recruitment channel (UKE/Self-help group/Social media/Online search/Medical practitioner/Physiotherapy practice/Friends, acquaintances/Other)
- Overall somatic symptom severity (PHQ-15)
- Long COVID symptoms (PHQ-15 PAIS)
- Fatigue (CFS)
- Post-exertional malaise (DSQ-PEM)
- Pain (PDI)
- Illness-related anxiety (SSD-12)
- Treatment expectations (TEX-Q)
- Expectation of symptom severity (NRS)
- Expectation of symptom burden (NRS)
- Expectation of coping with symptoms (NRS)

Version 1.0 Page 13 of 18

- Depression severity (Patient Health Questionnaire-9 [PHQ-9])
- Anxiety severity (Generalized Anxiety Disorder-7 [GAD-7])

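### DSQ-PEM is tested only as a yes/no status; adding an analysis of its score, if it yields one, would recover information on severity at little cost

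*SAP*

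**What the plan says.** Section 1.3 lists the endpoint as "Post-exertional malaise measured with the DePaul Symptom Questionnaire Post-Exertional Malaise (DSQ-PEM) at 6 weeks, 3 months, and 6 months". Unlike the entries for fatigue and pain, it is not worded as a change from baseline. Section 5.1.1 also lists DSQ-PEM among the baseline characteristics, between fatigue (CFS) and pain (PDI), without response categories.

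Section 5.3.2 splits the secondary endpoints in two. PHQ-15, CFS, PDI and PHQ-15 PAIS go into the linear mixed model for change. For the rest it says: "Dichotomous endpoints (Improvement of Long COVID symptoms, DSQ-PEM, DSM-5, B-IPQ) will be analysed with a mixed logistic model". In that model the outcome is the status at each visit. The model otherwise follows the primary one in section 5.3.1, which drops the group-by-time interaction when its test gives p≥0.05.

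The SAP states no scoring rule or cut-off for DSQ-PEM; these may stand in the protocol. Section 3.1 makes all analyses beyond the primary one exploratory and unadjusted.

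**The concern.** DSQ-PEM is a symptom questionnaire, yet the only planned test reduces it to present or absent. The logistic model sees a patient only when the status changes or differs between arms. An intervention that made PEM milder, or aggravated it, without moving patients across the threshold would leave the odds ratio unchanged.

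The trial enrols patients with PHQ-15 of at least 10, so a high proportion with PEM is plausible, though the SAP gives no figure. The higher that proportion, the less a binary status can distinguish the arms, and the harder a null result is to read: it could mean no effect, or an effect on severity that the status does not capture.

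**Working it through.** **Inputs from the SAP (section 2.3).** "A between-group effect size of d=0.5 is expected between COV.EXPECT and TAU for the change from baseline in the PHQ-15 score at 3 months"; "with a power of 80% and using a two-sided alpha of 5%, 64 patients in each group will be required". For dropout: "Assuming a loss to follow-up between baseline and 3 months (time point for primary outcome) of 25%, this results in N=258 randomised patients".

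**Inputs assumed.** DSQ-PEM gives a graded, roughly normal score. The treatment shifts that score by 0.5 SD, a value borrowed from the PHQ-15. The TAU proportion with PEM at follow-up ranges from 50% to 95%.

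**1. The SAP's own figure.** The two-sample t-test with d=0.5 has power 79.5% at 63 per arm and 80.1% at 64 (normal approximation at 64: 80.7%). For dropout, 64/0.75 = 85.3, rounded up to 86 per arm, and 3 × 86 = 258. Both figures reproduce.

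**2. The same shift, read as yes/no at one visit.** If a proportion p of TAU is above the cut, the active arm has p₂ = Φ(Φ⁻¹(p) − 0.5). With n = 64 and p̄ the mean of p and p₂:

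power = Φ( [ (p − p₂)√n − 1.96·√(2p̄(1 − p̄)) ] / √(p(1 − p) + p₂(1 − p₂)) )

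Example for p = 0.60 (unrounded 0.5987 and 0.4013): (0.1974 × 8 − 1.96 × 0.7071)/0.6932 = 0.279, and Φ(0.279) = 61.0%.

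| TAU with PEM | Active arm | Yes/no power | Loss against 80.1% | n per arm for 80% |
|---|---|---|---|---|
| 50% | 30.9% | 59.9% | 20 points | 102 |
| 60% | 40.3% | 61.0% | 19 points | 100 |
| 70% | 51.0% | 59.7% | 20 points | 103 |
| 80% | 63.4% | 55.2% | 25 points | 115 |
| 90% | 78.3% | 44.2% | 36 points | 152 |
| 95% | 87.4% | 32.8% | 47 points | 217 |

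A search over all cuts puts the best one at about 60% in TAU, so 61% is the single-visit maximum under these inputs. A simulation of 40,000 runs with a Wald test of the log odds ratio gave 60%, 59%, 61%, 55% and 44% at TAU proportions of 50% to 90%. At d=0.3 the score has 39% power and the status 14% to 27%.

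**3. Baseline adjustment, one visit.** With baseline correlation 0.5 and baseline included in both models, simulated power was 90% for the score, against 64%, 58% and 43% for the status at TAU proportions of 60%, 80% and 90%. Adjustment does not close the gap.

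**4. Visits pooled.** If the interaction is dropped, the treatment effect is averaged over visits: two in the first analysis, three after final lock. Take three visits, correlation 0.5, d=0.5 at each visit, adjusted for baseline. The variance of a patient's mean score is (1 + 2 × 0.5)/3 − 0.5² = 0.417, so the effective d is 0.5/√0.417 = 0.775. The power is then Φ(0.775 × √32 − 1.96) ≈ 99%. The simulated yes/no power in that setting is 93% at a 60% TAU proportion and 87% at 80%, a loss of 6 and 12 points. Over correlations of 0.3 to 0.7 and proportions of 60% to 90%, the loss ran from about 9 to 32 points with two visits and about 6 to 25 with three.

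**5. Scale of d.** Steps 2 to 4 take d in SD units of the follow-up score. The SAP states it for the change. If d=0.5 refers to the SD of change, the follow-up shift is 0.5·√(2(1 − ρ)), where ρ is the baseline to follow-up correlation: 0.592 at ρ = 0.3, 0.5 at ρ = 0.5 and 0.387 at ρ = 0.7. At an 80% TAU proportion the single-visit yes/no power is then 70%, 55% and 36%. The 61% maximum therefore belongs to ρ = 0.5 or to d on the follow-up scale. At ρ = 0.3 the status reaches about 75% at a 70% TAU proportion. The baseline-adjusted score analysis then has Φ(0.592/√(1 − 0.09) × √32 − 1.96) ≈ 94%.

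**The case against.** The strongest reply is that the choice is consistent and legitimate. Section 1.3 leaves out change from baseline for DSQ-PEM, as it does for the SCID-5 diagnosis, and section 5.3.2 then models status. Having PEM or not is a meaningful outcome, and the endpoint is exploratory with no power claim attached. All of that stands. The conflict in the quoted sentence concerns the B-IPQ, which section 1.3 defines as a change from baseline; that is a separate matter.

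The numerical premise is also open to challenge. The SAP nowhere describes a graded DSQ-PEM total. If status comes from a rule over several items rather than from a cut on one total, the normal-shift model is only a rough guide. The absence of categories in section 5.1.1 proves little, because instruments there are generally listed by name alone. This stands as well and makes the fix conditional on a usable score.

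Two stronger readings are tempting and are not supported:

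- A reader might infer that at least about 20 points of power are lost whatever happens. That is roughly the single-visit minimum at a borrowed effect size. The planned model is longitudinal, and once visits are pooled the loss can be as small as about 6 points.
- A reader might infer that worsening cannot register. Patients without PEM can still become positive, so this holds only when nearly everyone is positive, and the SAP does not give the prevalence.

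Section 5.1.2 also requires a descriptive analysis of the secondary endpoints, which might show scores, though it does not say so for DSQ-PEM.

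**Conclusion.** The point holds as a recommendation to add an analysis. As planned, changes in severity among patients whose PEM status does not change do not enter the test.

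Under the stated assumptions, single-visit power is at most 61% against about 80% for the score. With visits pooled the loss is about 6 to 32 points, depending on the number of visits, the correlation and the prevalence. Some loss remained in every scenario examined. These figures rest on a graded, roughly normal score, on an effect size the SAP gives only for the PHQ-15, and on assumed prevalences, so they show the order of magnitude and do not predict the trial's power for DSQ-PEM.

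The SAP does not contradict itself on DSQ-PEM, and the yes/no analysis is not wrong, so nothing here calls for removing it. The primary analysis is unaffected.

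**What to change.** In section 5.3.2, add DSQ-PEM to the endpoints analysed with the linear mixed model: change from baseline in the DSQ-PEM score at 6 weeks, 3 months and 6 months, with the baseline DSQ-PEM score as covariate, reporting mean differences with 95% confidence intervals at each visit. Keep the mixed logistic analysis of PEM status alongside it. Extend the entry in section 1.3 so that it names both the change in score and the status. If the instrument as used gives no usable score, say so in the SAP; the yes/no analysis then stands alone for a stated reason.

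The cost is a change of wording and one more run of a model already specified for CFS and PDI. No new data are needed. The downside is one further exploratory, unadjusted analysis and two DSQ-PEM results to report, which may not agree.

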5.3.6 Subgroup Analyses

The analysis of the subgroups is based on the FAS and thus is as close as possible to the ITT principle. Missing values are not imputed, but the implicit MAR assumption of the analysis model will be used.

Exploratory subgroup analyses will be performed for the primary endpoint by the appropriate interaction tests within the linear mixed regression model used within the primary analysis. The presented p-values are of descriptive nature only (two-sided tests). Relevant subgroups will be identified with a p-value for the interaction < 0.15 (EMA, 2019).

Predefined subgroups are:

- Age (young [≤first tercile] vs. middle aged vs. old [>third tercile])
- Gender (male vs. female)
- Education (≤ 10 years in school vs. > 10 years in school)
- Social support (number of people living in household ≤ 1 vs. > 1)
- Duration of Long COVID (< 1 year vs. ≤ 2 years vs. > 2 years)
- Severity of overall somatic symptoms at baseline (PHQ-15 score minimal/mild/moderate 0-14 vs. severe 15-30)
- Any chronic physical disease (SCQ-D)
- Any chronic mental illness (SCQ-D)
- Depression (PHQ-9 <10 vs. ≥10)
- Anxiety (GAD-7 <10 vs. ≥10)
- Biopsychosocial understanding of disease (yes vs. no; open question B-IPQ)
- Source of recruitment (University Medical Centre Hamburg-Eppendorf vs. Self-help group vs. Social media vs. Medical or physiotherapy practice vs. Other)
- Illness-related anxiety (SSD-12 < 24 vs. ≥ 24)
- Treatment expectations (TEX-Q <5 vs. ≥5)
- Alexithymia (TAS-20 <60 vs. ≥ 61)
- Emotion regulation (ERQ suppression split at median)

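### SAP section 5.3.2 treats the B-IPQ as a dichotomous endpoint, but section 1.3 defines it as a change from baseline; the single-visit SCID-5 diagnosis also needs its own model statement

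*SAP*

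**What the plan says.** **B-IPQ.** SAP section 1.3 lists as a secondary endpoint: "Change from baseline in symptom perception measured with the Brief Illness Perception Questionnaire (B-IPQ) at 3 months and 6 months". Section 5.3.2 gives the continuous list without it: "Continuous endpoints (PHQ-15, CFS, PDI, PHQ-15 PAIS) are analysed analogously to the primary endpoint". The B-IPQ appears instead in the next group: "Dichotomous endpoints (Improvement of Long COVID symptoms, DSQ-PEM, DSM-5, B-IPQ) will be analysed with a mixed logistic model". For that group, "the dependent variable is not the change from baseline, but the endpoint measurement at the respective time point".

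**SCID-5.** Section 1.3 places the somatic symptom disorder diagnosis at one visit: "Fifth Edition (DSM-5) (SCID-5) at 3 months". Section 5.3.2, where it is called DSM-5, gives it the same mixed logistic model, built by analogy with the primary model. According to section 5.3.1 that model has "time (categorical: 6 weeks and 3 months), the stratification variable gender as well as baseline PHQ-15 as fixed effects and patient as random effect", and also: "the interaction between time and random group is included and will be excluded from the model if the test result of the interaction is p≥0.05".

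**Other mentions of the B-IPQ.** Section 5.3.6 has a binary subgroup variable, "Biopsychosocial understanding of disease (yes vs. no; open question B-IPQ". Section 5.3.3 lists illness perception (B-IPQ) as a candidate risk factor. Section 5.7 records that the B-IPQ is the one SOMACROSS core measure kept as a secondary endpoint, and mentions no dichotomisation.

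**The concern.** For the B-IPQ, the two sections disagree on the type of variable, the dependent variable and the class of model. An analyst who follows section 5.3.2 needs a binary B-IPQ outcome that the SAP does not define. An analyst who follows section 1.3 must ignore section 5.3.2. The two routes answer different questions and could give different results. A SAP should close that choice before the data are seen, all the more for a measure close to the expectation and illness-anxiety mechanism that the trial studies.

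For SCID-5 the class of model is right, because a diagnosis is binary. What does not fit is the repeated-measures structure, since there is only one visit. Software may drop terms without notice, or report a subject-specific odds ratio that depends on a variance the data cannot supply.

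**Working it through.** **1. The plan's own figure.** Section 2.3 assumes d = 0.5, two-sided alpha 5% and power 80%.
- Normal approximation: n = 2(1.960 + 0.842)² / 0.5² = 62.8, so 63 per group.
- Noncentral t: 63 per group gives 79.5% and 64 gives 80.1%, so 64 per group and N = 192.
- 25% loss: 64 / 0.75 = 85.3, so 86 per group, and 3 × 86 = 258.

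The stated figures reproduce. They concern the PHQ-15 only, and nothing below changes them.

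**2. B-IPQ, sections side by side.** No arithmetic is needed.

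| | Section 1.3 | Section 5.3.2 |
|---|---|---|
| Type | change score | dichotomous |
| Dependent variable | change from baseline | value at the visit, not the change |
| Model implied | linear, as for CFS, PDI, PHQ-15 PAIS | mixed logistic |
| Binary rule | none | none |

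Where section 5.3.6 splits other questionnaires, it gives the rule: PHQ-9, GAD-7, SSD-12, TEX-Q and TAS-20 by cut-off, ERQ suppression at the median. There is no such rule for the B-IPQ endpoint.

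**3. SCID-5, fixed effects with one visit.** Columns: intercept, two group indicators, time, two time-by-group products and sex, 7 in all. With only the 3-month visit, the time column repeats the intercept and each product repeats its group indicator. Three columns are redundant, so the rank is 7 − 3 = 4. Baseline PHQ-15 was left out of this check; adding it would raise columns and rank by one each and leave the three redundancies.

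**4. SCID-5, random effect with one record per patient.** One data set of 3 × 64 patients was simulated, with event rates assumed for the purpose. The random-intercept standard deviation (SD) was fixed at a series of values and the remaining terms (treatment and sex) were refitted.

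| SD | Log-likelihood | OR, COV.EXPECT vs TAU |
|---|---|---|
| 0 | −126.09 | 0.36 |
| 1 | −126.08 | 0.29 |
| 2 | −126.07 | 0.18 |
| 3 | −126.06 | 0.11 |
| 5 | −126.06 | 0.03 |

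The likelihood is almost flat while the odds ratio changes more than tenfold, so the data do not in practice determine the SD. At SD = 0 the model is an ordinary logistic regression.

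**5. Cost of dichotomising, illustration only.** Assume a normal score split at the median. The information kept is 2/π = 0.637, so about 36% is lost. If the B-IPQ effect were also d = 0.5 (the SAP gives none), the proportions either side of the split would be Φ(0.25) = 0.599 and Φ(−0.25) = 0.401. Power would fall from 80% to 61% at 64 per arm, and from 90% to 74% at 86 per arm.

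**The case against.** - **Both endpoints are exploratory.** Section 3.1 makes every analysis beyond the primary one exploratory, and the repair is wording. This stands and limits the severity.
- **The B-IPQ open question may have been meant.** It is already coded yes/no for subgroups, so no cut-off would be needed. That is possible, but then the definition in section 1.3 is wrong, and the two sections still conflict.
- **A binary rule may stand in the protocol, which is not at hand.** This stands against any claim that a cut-off would have to be invented after data collection; the SAP does not show that. It also gives no binary rule for the DSQ-PEM, so the missing rule alone is not the point. The difference is that section 1.3 calls the B-IPQ a change from baseline and does not say so of the DSQ-PEM. A rule elsewhere would not remove that contradiction.
- **Analogy lets the analyst drop terms that do not apply.** For SCID-5 this is a fair reading, and it leads to ordinary logistic regression. It makes the SCID-5 point a clarification. It does not help the B-IPQ, because no analogy turns a change score into a yes/no outcome.
- **The B-IPQ may not be modelled at the first analysis.** Section 2.5 names all secondary endpoints only for the final analysis, when two post-baseline B-IPQ visits exist. A single-visit problem for the B-IPQ at the 3-month lock is therefore conditional.

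**Conclusion.** The B-IPQ contradiction between sections 1.3 and 5.3.2 is established from the text and rests on no assumption. As written, section 5.3.2 would analyse a different endpoint from the one defined. The SCID-5 mismatch is real for the model read literally, but secondary and easily repaired. This is a should-fix: two exploratory endpoints are affected, and the primary analysis and the sample size are not.

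A reader might infer more, and the document does not support it:
- That neither endpoint can be analysed correctly. SCID-5 is properly binary and becomes analysable once the inapplicable terms are dropped.
- That the SCID-5 model would fail to converge. The check shows a variance that is not identified, in one simulated data set with assumed rates; it does not show a failure to converge.
- That the trial would lose 36% of its B-IPQ information, about 122 of 192 patients remaining (0.637 × 192). That needs a normal score and a median split, neither of which is in the SAP, and it pools three arms although section 2.3 sizes a comparison of two.

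**What to change.** 1. In section 5.3.2, move the B-IPQ to the continuous list. Analyse its change from baseline, adjusted for baseline B-IPQ, with the linear mixed model at 3 and 6 months. If it is also analysed at the 3-month lock, specify ANCOVA there, as only one post-baseline visit exists then.
2. If a binary B-IPQ endpoint was really intended, leave section 5.3.2 and rewrite section 1.3 with its exact definition (which item or score, and which rule). Record the change in section 5.7 if it departs from the protocol.
3. State that SCID-5 somatic symptom disorder at 3 months is analysed by ordinary logistic regression on treatment, gender and baseline PHQ-15, without time, time-by-group or patient random effect.

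The cost is a few words in the SAP, settled before the affected analyses are run. No new data and no change of design are needed.
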